## Protocol Synopsis

Protocol Number:	ADCT-502-101
Title:	A Phase 1, Open-Label, Dose-Escalation Study to Evaluate the Safety, Tolerability, Pharmacokinetics, and Antitumor Activity of ADCT-502 in Patients with Advanced Solid Tumors with HER2 Expression
Sponsor:	ADC Therapeutics SA
Study Phase:	Phase 1
Indication:	
Five (5) types of patients, based on HER2 expression levels and mutations, are selected in this FIH study of ADCT-502:
 

1. Patients with indications and HER2 expression levels that qualified them for (prior) treatment with trastuzumab and/or ado-trastuzumab emtansine, e.g., HER2 positive BC and HER2 positive G/GE cancer.

2. Patients with BC or G/GE cancer with HER2 expression that is present, but at a level that is below the threshold qualifying them for Item Number 1.

3. Patients with HER2 expression levels equivalent to Item Number 1, but who have a tumor type other than BC or G/GE cancer (NSCLC, small cell lung cancer (SCLC), CRC, bladder, pancreatic, biliary tract, prostate, ovarian, endometrial, and salivary gland cancer).

4. Patients from the same indication list as in Item Number 3, except with HER2 expression levels present but lower than that, i.e. equivalent to expression levels in Item Number 2.

5. Patients with 1 of the 12 indications mentioned in Items 1–4 who have been shown to possess a HER2 hotspot mutation; they are either classified as HER2-high if a concomitant amplification was demonstrated, otherwise they are classified as HER2-low. Patients with such HER2 genetic alteration pre-defined prior to study enrollment and not belonging to 1 of the 12 indications may be included in the dose escalation part after sponsor agreement.

Rationale:	
The mechanism of action and preclinical data of ADCT-502 supports its use in patients with relapsed or refractory metastatic breast and gastric cancer who have been previously treated with trastuzumab/T-DM1. Given the substantial prevalence of HER2 expression in a range of other advanced cancers, including NSCLC, bladder, biliary tract, and ovarian cancer, for which HER2 targeted therapies are not licensed, ADCT-502 will also be evaluated as an anticancer treatment in patients with such tumor types for which there is published clinical evidence of HER2 expression. Also, there is high unmet medical need in breast and gastric/GE junction cancers in which HER2 expression is observed but below the defined thresholds for HER2 targeted therapy.
 
Results of preclinical studies in PDX suggest that ADCT-502 may have potent clinical activity in both groups of patients, those with HER2-positive/high tumors as well as those [REDACTED]

**Objectives:**

**Primary Objectives**

- Evaluate safety, tolerability, and determine the MTD and/or RDE of single agent ADCT-502 in patients with advanced solid tumors with known HER2 status (IHC  $\geq 1+$  or HER2 amplified/mutated) (Part 1).
- Further evaluate safety and tolerability at the dose level determined in Part 1 in patients with advanced solid tumors including breast cancer, lung, gastroesophageal, and bladder cancer or a basket of other solid tumors known to express HER2 (HER2-high or HER2-low status confirmed prospectively for study entry) (Part 2).

**Secondary Objectives**

- Evaluate the preliminary antitumor activity of ADCT-502.
- Characterize the PK profile of ADCT-502.
- Determine the immunogenicity of ADCT-502.

**Patient Selection:**

**Inclusion Criteria**

1. Male or female age 18 years or older.
2. Refractory to or intolerant of existing therapy(ies) known to provide clinical benefit for their condition.
3. Eastern Cooperative Oncology Group (ECOG) performance status:
  - a. Part 1: 0-2
  - b. Part 2: 0-1
4. Availability of formalin-fixed paraffin-embedded (FFPE) tumor tissue block (or unstained slides (minimum 7; 10 preferred) if block is not available) to demonstrate HER2 expression.

**Note:** any biopsy since initial diagnosis is acceptable, but if several are available, the most recent sample is preferred.

5. Pathologic diagnosis of solid tumor malignancy that is locally advanced or metastatic at time of Screening:

**Part 1 (Dose Escalation):**

Advanced solid tumors with documented HER2 status of IHC  $\geq 1+$  or HER2 amplified/mutated by FISH or NGS.

**Note:** Clinical pathology report of HER2 status must be available for review to confirm eligibility in Part 1.

**Part 2 (Dose Expansion):**

HER2-high\* or HER2-low\*\* advanced solid tumor belonging to one of the pre-specified indications for groups A – E (breast cancer, gastric & gastroesophageal cancer, bladder cancer, non-small cell lung cancer) or one of the eight pre-specified indications for the basket group

(SCLC, CRC, pancreatic, biliary tract, prostate, ovarian, endometrial, or salivary gland) according to assigned treatment group for which HER2 status has been confirmed prospectively (HER2-high or HER2-low) for study entry.

\* A HER2-high patient is defined as IHC 3+, or IHC 2+ with FISH amplification.

\*\* A HER2-low patient is defined as IHC 1+, or IHC 2+ without FISH amplification.

Note: A patient with IHC 0 / IHC 1+ with amplification is HER2-high for study purposes; a patient with IHC 3+ with negative amplification results is HER2-low for study purposes.

6. Part 2/Dose Expansion Only: Measurable disease as defined by Response Evaluation Criteria in Solid Tumors (RECIST) version 1.1.

Note: Lytic bone lesions or mixed lytic-blastic lesions, with identifiable soft tissue components, that can be evaluated by cross sectional imaging techniques such as CT or MRI can be considered as measurable lesions if the soft tissue component meets the definition of measurability per RECIST.

7. Screening laboratory values within the following parameters:

- a. Absolute neutrophil count (ANC)  $\geq 1500/\text{mm}^3$  ( $\geq 1.5 \times 10^9/\text{L}$ ).
- b. Platelet count  $\geq 100,000/\text{mm}^3$  ( $\geq 100 \times 10^9/\text{L}$ ).
- c. Hemoglobin  $\geq 9 \text{ g/L}$  ( $\geq 5.6 \text{ mmol/L}$ ).
- d. Aspartate transaminase (AST) and alanine aminotransferase (ALT)  $\leq 2.5 \times$  upper limit of normal (ULN); or  $\leq 5.0 \times$  ULN if liver metastases are present.
- e. Total bilirubin  $\leq 1.5 \times$  ULN (or  $\leq 3 \times$  ULN, with direct bilirubin  $\leq 1.5 \times$  ULN, in patients with known Gilbert syndrome).
- f. Serum/plasma creatinine  $\leq 1.5 \times$  ULN; or, if creatinine  $> 1.5 \times$  ULN, a measured creatinine clearance must be  $> 60 \text{ mL/min}$  as calculated by the Cockcroft and Gault equation for patient to be eligible.

8. Women of childbearing potential\* must agree to use a highly effective\*\* method of contraception from the time of giving informed consent until at least 16 weeks after the last dose of ADCT-502. Men with female partners who are of childbearing potential must agree that they or their partners will use a highly effective method of contraception from the time of giving informed consent until at least 16 weeks after the patient receives his last dose of ADCT-502.

\*Defined as: Sexually mature women who have not undergone bilateral tubal ligation, bilateral oophorectomy, or hysterectomy; or who have not been postmenopausal (i.e., who have not menstruated at all) for at least 1 year.

\*\*Defined as: Hormonal contraceptives (oral, injectable, patch, intrauterine devices), male partner sterilization, or total abstinence from heterosexual intercourse, when this is the preferred and usual lifestyle of the patient.

**Note:** The double-barrier method (e.g., synthetic condoms, diaphragm, or cervical cap with spermicidal foam, cream, or gel), periodic abstinence (such as calendar, symptothermal, post-ovulation), withdrawal (coitus interruptus), lactational amenorrhea method, and spermicide-only are not acceptable as highly effective methods of contraception.

#### **Exclusion Criteria**

1. Known history of  $\geq$  Grade 3 hypersensitivity to a therapeutic antibody.
2. Known history of positive serum human ADA to trastuzumab.
3. History of Stevens-Johnson syndrome or toxic epidermal necrolysis syndrome.
4. Major surgical procedure or significant traumatic injury, radiotherapy, chemotherapy, targeted therapy, hormone therapy (except for luteinizing hormone-releasing hormone (LHRH) agonists or denosumab) or other anticancer therapy within 21 days OR within 5 half-lives of the product, whichever is shorter, prior to the Cycle 1, Day 1 visit.

**Note:** cumulative dose of anthracycline  $>450 \text{ mg/m}^2$  is prohibited.

5. Failure to recover to Grade 0 or Grade 1 from acute non-hematologic toxicity due to previous therapy, prior to screening (with the exception of alopecia).
6. Central Nervous System (CNS) disease only.
7. Symptomatic CNS metastases or evidence of leptomeningeal disease (brain MRI or previously documented cerebrospinal fluid (CSF) cytology).

Previously treated asymptomatic CNS metastases are permitted provided that the last treatment (systemic anticancer therapy and/or local radiotherapy) was completed  $\geq 8$  weeks prior to Day 1 except usage of low dose of steroids on a taper (i.e. up to 10 mg on Day 1 and consecutive days is permissible if being tapered down). Patients with discrete dural metastases are eligible.

8. Active cardiac disease including any of the following:
  - Angina pectoris that requires the use of anti-anginal medication.
  - Ventricular arrhythmias except for benign premature ventricular contractions.
  - Supraventricular and nodal arrhythmias requiring a pacemaker or not controlled with medication.
  - Clinically significant valvular disease with documented compromise in cardiac function.
  - Symptomatic pericarditis.
  - Congenital long QT syndrome or a corrected QTc [QTcF] interval  $\geq 450 \text{ ms}$  at Screening.
  - LVEF  $< 50\%$  at Screening or a history of decrease in LVEF to  $< 40\%$  during previous treatment with HER2 targeted therapy.
9. History of clinically significant cardiovascular dysfunction including any one of the following:
  - History of myocardial infarction (MI) or recent MI documented by elevated cardiac enzymes or persistent regional wall abnormalities on

assessment of left ventricular function within 6 months prior to Day 1.

- History of documented congestive heart failure (New York Heart Association functional classification III-IV).
  - Documented cardiomyopathy.
  - Uncontrolled hypertension (systolic blood pressure  $>180$  mm Hg or diastolic blood pressure  $>100$  mm Hg).
10. Active ulceration of the upper gastrointestinal tract or gastrointestinal bleeding.
  11. Active autoimmune disease, motor neuropathy considered of autoimmune origin, and other CNS autoimmune disease.
  12. Patients receiving concomitant immunosuppressive agents or chronic corticosteroids use, at study entry except in cases outlined below:
    - Topical applications (e.g. rash), inhaled sprays (e.g. obstructive airways diseases), eye drops or local injections (e.g. intra-articular), or as physiologic replacement, are permitted.
  13. Known human immunodeficiency virus (HIV) infection; known seropositive for hepatitis B surface antigen (HBsAg), or antibody to hepatitis C virus (anti-HCV) with confirmatory testing and requiring anti-viral therapy.

**Note:** Testing is not mandatory to be eligible. Testing for HCV should be considered if the patient is at risk for having undiagnosed HCV (e.g., history of injection drug use).
  14. Any other malignancy within 3 years prior to Day 1, with the exception of adequately treated in-situ carcinoma of the cervix uteri, basal or squamous cell carcinoma or other non-melanomatous skin cancer.
  15. Active bleeding diathesis or significant anticoagulation (such as with an oral anti-vitamin K medication. Low-dose warfarin, aspirin, or equivalent, are permitted as long as the INR  $\leq 2.0$ ).
  16. History of thromboembolic or cerebrovascular events within the last 6 months, including transient ischemic attack, cerebrovascular accident, deep vein thrombosis or pulmonary embolism.
  17. Clinically significant third space fluid accumulation (i.e., ascites requiring tap or pleural effusion that is either requiring tap or associated with shortness of breath).
  18. Breastfeeding or pregnant.
  19. Other concurrent severe and/or uncontrolled medical conditions (e.g., uncontrolled diabetes mellitus, active untreated or uncontrolled infection including viral and systemic fungal infections, chronic obstructive or chronic restrictive pulmonary disease including dyspnea at rest from any cause) that could cause unacceptable safety risks or compromise compliance with the protocol.

#### Study Design:

This is a first-in-human (FIH) Phase 1, multicenter, open-label study to evaluate the safety, tolerability, PK, pharmacodynamics (PD), immunogenicity, and preliminary antitumor activity of ADCT-502 used as a single agent in patients with advanced solid tumors with documented HER2 expression. The study consists of two parts.

During Part 1 (Dose Escalation), patients will receive escalating doses of

ADCT-502 according to a modified continual reassessment method (mCRM) to determine the MTD and/or RDE.

Patients participating in Part 2 (Dose Expansion) will have their HER2 status prospectively measured to be classified as either HER2-high or HER2-low as defined for the study and assigned to 1 of 9 groups as follows:

- Group A: HER2-high breast cancer
- Group B: HER2-low breast cancer
- Group C: HER2-high gastric/GE cancer (and staggered HER2-low)
- Group D: HER2-high bladder cancer (and staggered HER2-low)
- Group E: HER2-high NSCLC (and staggered HER2-low)
- Group F: Basket of 8 HER2-high solid tumor indications (SCLC, CRC, pancreatic, biliary tract, prostate, ovarian, endometrial, or salivary gland)

The proposed indication for Group C (HER2-high gastric/GE cancer) may be exchanged with the indication of Group D or E (HER2-high bladder cancer or NSCLC), or one of the indications from the basket group, depending on emerging data from Part 1.

Simon's 2-Stage design will be used during Part 2. Enrollment will be paused and a futility analysis performed after Stage 1. If futility is not triggered, enrollment for that group will continue to Stage 2.

Groups A, B, and C will be opened for enrollment simultaneously. If for one or more of Groups A, B, or C futility is not triggered, Groups D, E, and F will be opened.

If futility for the HER2-high patients enrolled in Stage 1 of Groups C, D, or E is not triggered, enrollment of HER2-low expressing patients in the respective group will be opened.

This recruitment of HER2-low patients in indications of Groups C, D and E is also subject to a Simon 2-stage design.

The duration of each patient's participation will be dependent on individual response to treatment and will include a Screening Period (of up to 28 days), Treatment Period, and Follow-up Period. Patients may continue treatment until disease progression or unacceptable toxicity.

All patients will have an end of treatment (EOT) visit as soon as possible after decision to discontinue ADCT-502 and prior to initiation of new anticancer treatment. If possible, patients will have an additional follow-up visit 12 weeks after the last dose of ADCT-502 for collection of PK, soluble HER2, and ADA samples, unless a new anticancer treatment has been initiated.

All patients will be followed approximately every 12 weeks after the last dose of study drug to collect survival information. Follow-up for survival may continue for up to 2 years after treatment discontinuation.

Any patients who discontinue treatment for any reason other than disease progression will continue to be followed by radiographic examination every 12 weeks until disease progression or initiation of new anticancer treatment.

The duration of the study participation for each patient is defined as the time from the date of signed written informed consent through the completion of the follow-up period, or withdrawal of consent.

#### **Estimated Duration of Patient Participation and Study Duration:**

**Efficacy Assessments:**

Study duration will be dependent on overall patient tolerability and response to treatment. It is anticipated that the entire study (Part 1 and Part 2) could be approximately 3 years from first patient treated to last patient completed.

Computerized tomography (CT) or magnetic resonance imaging (MRI) scans with contrast of the chest, abdominal and pelvic area or brain scans (CT or MRI with contrast), and bone scans or X-ray exam if clinically indicated, will be performed. For image acquisition specifications, including instruction in the event of allergy to contrast dye, refer to Appendix II of RECIST version 1.1 (Specifications for Standard Anatomical Radiological Imaging).

The same methods used at Baseline which identify sites of disease should be used uniformly for all subsequent assessments. Response to treatment will be determined by the Investigator as complete response (CR), partial response (PR), stable disease (SD), or progressive disease (PD) according to RECIST version 1.1.

**Pharmacokinetic, Pharmacodynamic, and Other Exploratory Assessments:****Pharmacokinetics**

The PK profile of ADCT-502 (total antibody), pyrrolobenzodiazepine (PBD)-conjugated antibody, and free warhead SG3199 will be assessed centrally. The PK profile will include determination of standard PK parameters

(e.g., maximum concentration [ $C_{max}$ ], time to  $C_{max}$  [ $T_{max}$ ], area under the curve [AUC]).

**Safety Assessments:**

The safety objective will be evaluated by summarization of AEs, SAEs, and changes in laboratory parameters, vital signs, ECGs, and MUGA/echocardiograms. Dose interruptions, reductions, and relative dose intensity will also be summarized. Adverse events will be graded according to CTCAE version 4.0.

**Definition of DLT**

A DLT is defined as any of the following events that occur during the 21-day DLT evaluation period, except those that are clearly due to underlying disease or extraneous causes.

A hematologic DLT is defined as:

Event	Severity
Febrile neutropenia or neutropenic infection	Grade 3 or 4
Neutropenia lasting > 7 days	Grade 4
Thrombocytopenia	Grade 4
Thrombocytopenia with clinically significant bleeding	Grade 3
Thrombocytopenia requiring a platelet transfusion	Grade 3

Anemia	Grade 4
Anemia requiring transfusion	Grade 3

A **non-hematologic** DLT is defined as:

Event	Severity
Hy's law case	AST and/or ALT > 3x ULN and bilirubin > 2x ULN, and without initial findings of cholestasis (serum alkaline phosphatase (ALP) activity < 2x ULN) and no other reason that could explain the combination of increased transaminases and serum total bilirubin, such as viral hepatitis A, B, or C, preexisting or acute liver disease, or another drug capable of causing the observed injury.
Hypersensitivity/infusion-related reaction (regardless of premedication)	Grade 3 or higher. A Grade 3 hypersensitivity / infusion-related reaction that resolves within 24 hours after onset with appropriate clinical management does not qualify as a DLT.
All other non-hematologic toxicity	Grade 3 & 4.

The following conditions **are not** considered non-hematologic DLTs:

Event	Severity
Fatigue	Grade 3 for $\leq$ 7 days.
Diarrhea, nausea, or vomiting	Grade 3 in the absence of premedication that responds to therapy and improves by at least 1 grade within 3 days for Grade 3 events or to $\leq$ Grade 1 within 7 days.
Serum lipase or serum amylase	Grade 3 for $\leq$ 7 days if without clinical signs or symptoms of pancreatitis.
Electrolyte abnormalities	$\leq$ Grade 3 which normalize within 48 hrs (with or without medical intervention) and which do not manifest themselves clinically; in such instance, a follow-up sample MUST be taken within 48 hrs to check whether such normalization has occurred.

**Investigational**

ADCT-502 is a sterile formulation containing PBD-conjugated humanized

**Product, Dosage, and Mode of Administration:**

monoclonal IgG1 antibody (DAR  $1.8 \pm 0.3$ ) and engineered trastuzumab (DAR = 0). ADCT-502 is formulated as a sterile liquid at 5 mg/mL in a 10 mL glass vial (2.0 mL nominal fill). The drug product is designed to deliver 10 mg ADCT-502 per vial and is intended for intravenous infusion following dilution in 0.9% sodium chloride

Patients will receive a 1-hour IV infusion of ADCT-502 on Day 1 of each 3-week (21-day) cycle. If ADCT-502 is well tolerated after the first cycle, the infusion duration may be shortened to 30 minutes for subsequent cycles for that patient at the discretion of the Investigator.

**Part 1 (Dose-Escalation Design):**

Each cohort will consist of 2 patients. There will be a 24-hour observation before enrolling the second patient at Dose Level 1. The DLT observation period at each dose level is 1 cycle (3 weeks), after which it will be determined whether to escalate to the next dose level, stay at the current dose level, or de-escalate to the previous dose level for the next cohort.

There will be no de-escalation from Dose Level 1. Intrapatient dose escalation is not permitted.

Dose escalation is not permitted unless two or more patients have complete DLT information through the first cycle in any given dose level.

Dose escalation will be determined by using a mCRM with a target DLT rate of 30% and an equivalence interval of 20% to 35%, and with dose escalation-with-overdose-control (EWOC) and no dose skipping.

The mCRM will be implemented in Part 1 under the oversight of a Dose Escalation Steering Committee (DESC). The DESC will confirm each escalating dose level after reviewing all available safety data. The PK data from patients in that dose level and prior dose levels may also inform DESC decision making. The DESC may halt dose escalation prior to determining the MTD based on emerging PK, PD, toxicity, or response data.

Additional patients may be included at any dose level to further assess the safety and tolerability if at least 1 patient in the study has achieved a partial response or better, or if further evaluation of PK or PD data is deemed necessary by the DESC to determine the RDE.

Furthermore, to better understand the potential efficacy of ADCT-502 in an indication approved for treatment with HER2 targeted antibodies, up to 3 additional breast cancer patients who have previously been treated with an approved HER2 targeted therapy may be enrolled per cohort at given dose levels  $\geq 60 \mu\text{g/kg}$  determined by the mCRM model to be safe.

Dose escalation will be stopped after the mCRM has assigned 3 cohorts consecutively to the same dose level.

If the MTD is not reached, the recommended dose for expansion (RDE) will be determined.

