### 18.4.2 Model and Priors

Dose escalation in this study will be conducted using the mCRM.

For each dose,  $d = 1, \dots, n$ , we model the binary outcome of non-DLT, or a DLT.

The log odds of a DLT are modeled as

$$\theta_d = \log\left(\frac{\pi_{DLT}}{1 - \pi_{DLT}}\right)$$

with a 2-parameter model

$$\theta_d = \alpha + \exp(\beta) \log(d_i / d^*)$$

where  $d^*$  is the reference dose, which is used to standardize the dose  $d_i$  and allows for the interpretation of  $\alpha$  as the odds of a DLT at  $d^*$ .  $\exp(\beta)$  is positive, ensuring a monotonically increasing dose-toxicity relationship.

[Neuenschwander, 2008](#) placed a bivariate lognormal prior on the two parameters and proposed eliciting information on the risk of DLT at two (2) or more doses to obtain prior means and variances. Several articles have examined the specification of priors. When there are no previous historical clinical data available, it is possible to use uninformative prior. For this purpose, the above model can be re-parametrized in terms of  $(\rho_0, \gamma)$ , where  $\rho_0$  is the probability of a DLT at the starting dose  $d_1$  and  $\gamma$  is the MTD, the dose expected to produce DLT at 0.3 probability in this study, with

$$\gamma = \exp(-\beta) * (\log(\theta_d) - \log(1 - \theta_d) - \alpha)$$

and placing the following independent prior distributions on the parameters.

$$\rho_0 \sim \text{Uniform}(0, 0.30)$$

$$\gamma \sim \text{Uniform}(d_1, d_n).$$

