### 18.4.3 Dose Escalation Rule and Choice of Cohort Size

Dose escalation will begin with 2 patients enrolled at the initial starting dose. The cohort size is 2, which means that 2 patients will be assigned to escalate to the next dose level, de-escalate to the prior dose level, or, stay at the current dose level.

On the completion of each cohort (i.e., 2 patients treated and assessed for DLT after 1-cycle), the posterior distributions of  $\theta(d)$  are summarized for each dose level by the probabilities of under-dosing, targeted toxicity, or excessive/unacceptable toxicity. These 3 probabilities are defined as:

$$\text{Under-dosing: } \theta_d \in (0, 0.20)$$

$$\text{Targeted Toxicity: } \theta_d \in [0.20, 0.35]$$

$$\text{Excessive or Unacceptable Toxicity: } \theta_d \in (0.35, 1]$$

The dose which maximizes the probability of targeted toxicity while controlling the probability of excessive or unacceptable toxicity to  $\leq 25\%$  will be recommended for the next cohort of 2 patients. The model has the flexibility for a larger cohort size if additional patient are available.

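### As printed, the dose-escalation model cannot respond to toxicity at the starting dose: it recommends the next level even after DLTs in both of the first two patients

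*Protocol*

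**What the plan says.** The Synopsis and Protocol 4.6 set the target and interval: "Dose escalation will be determined by using a mCRM with a target DLT rate of 30% and an equivalence interval of 20% to 35" per cent. They add "dose escalation-with-overdose-control (EWOC) and no dose skipping", and on size: "Each cohort will consist of 2 patients".

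Protocol 18.4.2 gives a two-parameter logistic model in log dose. It re-expresses the model through ρ0, the DLT probability at the starting dose, and γ, the MTD, "and placing the following independent prior distributions on the parameters": ρ0 uniform on 0 to 0.30, and γ uniform from the lowest to the highest dose (30 to 500 µg/kg in Table 9).

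The rule in 18.4.3 is: "The dose which maximizes the probability of targeted toxicity while controlling the probability of excessive or unacceptable toxicity to" 25% or less is recommended next. Excessive toxicity means a DLT rate above 0.35. Section 18.4.4.1 stops the trial if that probability exceeds 25% at the lowest dose.

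Sections 4.6 and 4.6.1 require the Dose Escalation Steering Committee (DESC) to confirm each escalation and let it modify the schedule. Section 2.2 says that recommendations rest on all DLT information to date. The SAP refers back to the protocol for the design and lists DLT data only, so it does not alter the model.

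**The concern.** With this prior, the data from the starting dose inform only ρ0, and ρ0 cannot exceed the target rate. Two consequences follow. The model learns nothing about the location of the MTD from the first cohort. And as DLTs push ρ0 towards 0.30, the fitted curve flattens, so higher doses look safer.

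In a first-in-human trial the first escalation recommendation would then not depend on the data, and the overdose probability put before the DESC would move the wrong way. The level above could also take up to 3 extra breast cancer patients per cohort, because those places are tied to levels "determined by the mCRM model to be safe", and 60 µg/kg meets the 25% limit whatever the first cohort shows.

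**Working it through.** **The plan's own figure.** The only numeric output printed for the escalation design is about 30 patients in Part 1 (12.1), without a derivation. Simulating the printed rule under the five scenarios of 18.4.5.1 gives mean sizes of 24.2, 27.5, 25.3, 28.8 and 26.4, broadly in line. This does not test the point below.

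**Inputs.** Model and priors from 18.4.2; rule from 18.4.3, reading its θ as a DLT probability; dose levels from Table 9; cohorts of 2; no skipping. After the first cohort the candidates are 30 and 60 µg/kg.

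**Model in terms of ρ0 and γ.** logit p(d) = logit ρ0 + (logit 0.30 − logit ρ0) × log(d/30) / log(γ/30).

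**Step 1: the MTD posterior.** At d = 30, p = ρ0 exactly. With y DLTs in 2, the likelihood is ρ0^y (1 − ρ0)^(2−y), which does not contain γ. The posterior of γ therefore equals its prior, with mean (30 + 500)/2 = 265 µg/kg for y = 0, 1 or 2.

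**Step 2: overdose probability at higher doses.** p(d) can exceed 0.35 only if γ < d. For fixed γ < d it does so only when ρ0 is low enough, because the slope shrinks to zero as ρ0 approaches 0.30. More DLTs move ρ0 upward, so P(p > 0.35) falls at every higher dose. Grid posterior:

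| Dose (µg/kg) | 0/2 | 1/2 | 2/2 |
|---|---|---|---|
| 30 | 0 | 0 | 0 |
| 60 | 0.045 | 0.036 | 0.030 |
| 120 | 0.125 | 0.096 | 0.077 |
| 300 | 0.334 | 0.241 | 0.186 |
| 500 | 0.543 | 0.378 | 0.284 |

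At 60 µg/kg the value can never exceed P(γ < 60) = 30/470 = 0.064, so that dose passes the 25% limit whatever happens at level 1.

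**Step 3: the decision.** P(target) at level 1 is P(0.20 ≤ ρ0 ≤ 0.30):
- 0/2: (0.8³ − 0.7³)/(1 − 0.7³) = 0.169/0.657 = 0.257
- 1/2: with F(r) = r²/2 − r³/3, 1 − F(0.2)/F(0.3) = 1 − 0.01733/0.036 = 0.519
- 2/2: 1 − (0.2/0.3)³ = 1 − 8/27 = 0.704

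At level 2 the same grid gives 0.407, 0.687 and 0.837. Level 2 is higher each time, so the rule recommends 60 µg/kg after every possible result. It still does so after 4/4 and 6/6.

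**Step 4: the scale of γ.** The text and prior of 18.4.2 make γ a dose, but its formula, combined with the log-dose model, gives a log-dose ratio. After 2/2, P(target) at level 2 is 0.760 with a dose-linear logit and 0.787 with γ uniform on log dose, against 0.704 at level 1. In the log-dose case P(p > 0.35) at 60 µg/kg is bounded by ln 2 / ln(500/30) = 0.246. All readings recommend escalation. The 10-level ladder of Section 2.4 does too.

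**Step 5: the safety stop.** Since ρ0 ≤ 0.30, P(ρ0 > 0.35) = 0 for any data, so the 18.4.4.1 condition can never be met.

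**Step 6: which feature is responsible.** Keeping the cap and the uniform margins but adding negative dependence between ρ0 and γ (Gaussian copula, correlations −0.5, −0.8 and −0.95, assumed) makes the MTD estimate respond: at −0.95 its mean is 291, 200 and 154 µg/kg after 0, 1 and 2 DLTs. The rule still goes to 60 µg/kg after 2/2 at all three correlations. With an uncapped logistic prior (illustration only: α ~ N(logit 0.3, 2²), β ~ N(0, 1), reference dose 240), P(p > 0.35) at level 1 becomes 0.42 after 1/2 and 0.87 after 2/2.

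**Step 7: how often it matters.** The scenarios set the level-1 DLT rate at 0.10, 0.05, 0.02, 0.10 and 0.13. P(at least one DLT in 2) = 1 − (1 − p)² = 0.19, 0.10, 0.04, 0.19 and 0.24. P(2/2) = p² runs from 0.0004 to 0.017. None of the five tests an over-toxic starting dose.

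**The case against.** The strongest reply is that the model only recommends. The DESC must confirm each escalation on all available safety data, and 4.6.1 lets it modify the schedule. That stands as mitigation: two DLTs in the first two patients would hardly go unnoticed. It does not repair a model output that becomes more reassuring at level 1 as toxicity appears, or a safety stop that cannot act.

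Three stronger readings are tempting, and the documents do not support them.

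- A reader might infer that overdose control fails at every level. With γ read as a dose and 0/2 at all lower levels, a first 1/2 does give escalation at levels 2-7 (2-6 with a dose-linear logit). But there the DLT raises the overdose probability at the next level, from 0.083 to 0.151 after level 2 and from 0.093 to 0.160 after level 7, as it should. With γ uniform on log dose, none of levels 2-7 escalates. A first 1/2 at level 7 is 1 DLT in 14 patients, and Section 2.2 intends the whole history to count. This is a design choice to disclose, not an error.
- Simulating the printed rule with γ as a dose, 58-88% of trials escalate at least once directly after a cohort with a DLT. That figure counts all levels and does not measure the starting-dose defect.
- A reader might infer that 300 µg/kg opens after two DLTs at 30 µg/kg, since 0.186 is under 25%. The bar on skipping prevents that for the next cohort.

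**Conclusion.** The point holds for the starting dose. As printed, the first model recommendation does not depend on the first cohort's data, the overdose probability at higher doses falls as starting-dose DLTs rise, and the 18.4.4.1 stop is inert. This contradicts the protocol's stated 30% target and overdose control. The unchanged MTD posterior and the inert stop are exact. The escalation decision rests on a grid posterior and holds on all three readings of γ. The value of 265 µg/kg belongs to the readings with γ uniform in dose.

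On the protocol's scenarios the defect would be exercised in about 4-24% of trials (any level-1 DLT) and in under 2% in its extreme form (2/2). It matters most if the starting dose is more toxic than any scenario assumes. The documents do not report what the first cohort showed, so nothing here implies that any patient was wrongly escalated.

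**What to change.** Reconcile 18.4.2 and 18.4.3 with the stated target, the overdose control and the 18.4.4.1 stop:

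1. Replace the prior with one that (i) lets the starting-dose DLT probability exceed 0.35 and (ii) links it to the MTD, so that starting-dose DLTs raise P(p > 0.35) at higher doses. Both parts are needed, because dependence alone with the cap kept leaves the 2/2 decision unchanged. Section 18.4.2 already cites a bivariate prior.
2. State the scale of γ consistently in the text, formula and prior.
3. Tabulate the model decision after 0/2, 1/2 and 2/2 at each level. This also discloses the behaviour at levels 2-7.
4. Re-run the five scenarios with at least one over-toxic starting dose added.

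If the prior is kept, state an explicit model constraint at the starting dose in 4.6 and 18.4.3, with its clinical content left to the sponsor.

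**Cost.** A prior change, one table and new simulations. The new prior needs calibration: under the vague illustrative prior in the working, no dose is admissible after even 1/2 at level 1. A starting-dose constraint that acts after any level-1 DLT would add one 2-patient cohort in about 4-24% of trials, or 2 × 0.04 to 2 × 0.24 = 0.1 to 0.5 patients on average. Extending such a constraint to all levels is a separate choice with a price: in Scenario 4, selection of a dose in the 20-35% range falls from 61% to 51% unless the three-cohort stop is recalibrated.
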